Assuming that 50% of the subjects in the control arm will not relapse during follow up,^{5 6} a 15% increase in this percentage due to intervention is clinically beneficial, and using a power of 90% and a significance level of 5%, a total sample size of 460 subjects will be required. This sample size is based on an analysis of time to relapse and will allow us to detect a 37% decrease in the hazard of relapse (hazard ratio of 0.63) in the intervention group using a Cox proportional hazards model. This sample size has been calculated using the Stata version 11⁷. The sample size is inflated by a factor of 1.06; assuming that the 120 care coordinators see an average of 4 service user participants in the trial and an intraclass correlation coefficient of 0.02, this gives a total sample size of 488. Finally, the sample size is inflated by 10% to account for drop outs (the primary outcome is obtainable from routine data), giving a total sample size of 544.

Randomisation

Participants were individually block randomised using blocks of size 2, 4 and 6 to either contingency management or optimised treatment as usual, stratified by severity of cannabis use (one to three times a week versus four or more times a week). Randomisation was carried out remotely and with impartiality by Sealed Envelope⁸.

Blinding

This was a single blind trial. Participants could not be blinded to their allocation as they will be participating in an interactive intervention. Outcome assessors were be blinded to allocation. However, this relied on participants, their care coordinators and clinical team not telling the assessors the.

The statisticians and health economists will remain blind to allocation until the primary analyses have been verified.

Outcomes

Primary Outcome

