The CONSORT¹⁻³ flow diagram will be constructed by/in collaboration with the Trial Manager who will have logs of service users who do and do not agree to take part in the study. It will include number of service users randomised to each arm of the trial, and the numbers who have follow up data available.

All analyses will be on an intention to treat basis and data from the pilot trial will be incorporated into the main trial.

Data will be analysed using Stata version 14¹⁵.

Descriptive statistics

Initial analyses will look at summary statistics for all variables, both overall and by randomised group. Summary statistics for continuous variables will be mean, median, SD, lower quartile, upper quartile, minimum and maximum and reported appropriately according to distribution. Summary statistics for categorical variables will be frequency and percentage within each category.

Summary statistics of baseline variables by whether a participant has dropped out of the study will also be examined to determine whether the drop outs had similar characteristics to those who remained in the study at baseline.

Analysis of the primary outcome

The primary outcome will be initially examined using Kaplan Meier survival curves by randomised allocation. If the assumptions of proportional hazards is satisfied, Cox Proportional Hazards modelling to compare the intervention and control groups will be carried out, adjusting for severity of cannabis use at baseline (the stratification variable, dichotomous – 1 to 3 times a week versus 4+ times a week) and whether the participant was part of the pilot trial. If the assumption of proportional hazards is not fulfilled, alternative modelling strategies will be employed. Robust standard errors will be used to account for clustering by therapist; which should account for most of the centre effects in this multicentre individually randomised trial. Hazard ratios and 95% confidence intervals will be presented.

Analysis of the secondary outcomes

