2. Analysis of the primary outcome excluding those participants who have no follow up secondary outcome data (for 12 weeks and 18 months separately) because those who drop out or die may be different to those who remain in the study and/ or survive. Before doing this, some demographic statistics comparing those who remained in the study and those who dropped out will be produced.
3. Analysis of those in the main trial only as some changes were made to the protocol at the end of the pilot before the main trial commenced, which might mean the participants behave differently to those in the pilot trial.
4. Analysis of the primary outcome controlling for the same factors as in the primary analysis plus the number of psychoeducation sessions attended (which is being offered in both arms of the trial).
5. Analysis of the primary outcome controlling for the same factors as the primary analysis and number of admissions in the six months prior to baseline.

6. Analysis of the primary outcome controlling for the same factors as the primary analysis, but using centre as the clustering variable not therapist.

There will be up to two supportive analyses for the number of admissions during follow up:

1. In addition to the factors included in the main analysis, this will include predictors of missingness.

2. Including those who were discharged within 18 months and assuming they had no admissions over the follow up time.

There may be supportive analyses for secondary outcomes collected at 18 months, as outlined in the missing data section.

Exploratory analysis:

We will investigate potential patterns and degree of non-compliance using clinical definitions of compliance and descriptive analysis. We will perform a Complier Average Causal Effect (CACE) analysis if feasible.

There are no subgroup analyses planned.

Health Economic analyses

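### The primary Cox model is valid, but moving admissions in the six months before baseline into it from supportive analysis 5 would give a small gain in power and protect against chance imbalance.

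*SAP*

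**What the plan says.** - **Outcome.** SAP, Primary Outcome: relapse is admission to hospital, a crisis house or a crisis resolution team, taken from Trust informatics data over the 18 months after baseline.
- **Primary model.** SAP, Analysis of the primary outcome: a Cox model "adjusting for severity of cannabis use at baseline" (the stratification variable, two levels) and for pilot membership, with robust standard errors for clustering by therapist.
- **Randomisation.** Stratified by cannabis severity alone, so the design does not balance earlier admissions.
- **Where earlier admissions appear.** SAP, Supportive analyses, item 5: the primary factors plus "number of admissions in the six months prior to baseline". The lead-in allows for as many as six supportive analyses and does not promise all of them. Item 5 gives no functional form and no rule for missing values.
- **Sample size.** "Assuming that 50% of the subjects in the control arm will not relapse during follow up", and "a 15% increase in this percentage due to intervention is clinically beneficial"; target "hazard ratio of 0.63"; "a total sample size of 460 subjects will be required" before inflation.

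**The concern.** Admission before baseline is the nearest baseline counterpart of an admission-based outcome. It is fixed before randomisation, and apart from the two primary covariates it is the only named baseline covariate in the supportive list for the primary outcome. The plan gives no reason for keeping it out of the primary model. In its health economic section the SAP does adjust for the baseline counterpart of the outcome: QALYs for baseline EQ-5D utility, and costs for baseline differences.

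If the variable predicts relapse, leaving it out of a Cox model pulls the treatment hazard ratio towards 1 and costs some power. It also leaves the main estimate exposed to whatever imbalance chance produced in this one trial. The SAP does not say how to read a difference between the primary result and item 5.

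**Working it through.** **1. The plan's own sample size.** Inputs from SAP, Sample size: 90% power, 5% significance (two-sided assumed), hazard ratio 0.63, relapse-free 50% v 65%; equal allocation assumed.

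- Events (Schoenfeld): 4 × (1.960 + 1.282)² / (ln 0.63)² = 197.
- Mean relapse probability: (0.50 + 0.35)/2 = 0.425, so 197/0.425 = 464 participants, against 460 stated.
- Clustering, from "an average of 4 service user participants in the trial and an intraclass correlation coefficient of 0.02": 1 + 3 × 0.02 = 1.06, and 460 × 1.06 = 487.6, so 488.
- Drop-out: 488/0.9 gives 543, against 544 stated.
- Power with 460 × 0.425 = 195.5 events at 0.63: 89.8%.

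The figures reproduce without the extra covariate.

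**2. Power with and without prior admissions.** The SAP gives neither the prevalence of prior admission nor its hazard ratio for relapse. Both are assumed here, with the variable taken as any v none. Simulations used 460 participants, constant hazards, no clustering and 2,000 trials per scenario (Monte Carlo standard error about 0.7 points for each power figure).

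- Set A fixes the marginal relapse-free proportions at 50% and 65%, which is how the SAP frames its target.
- Set B fixes control relapse at 50% and the covariate-conditional treatment hazard ratio at 0.63.

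| Set | Prevalence | Covariate HR | Power without | Power with | Gain (points) |
|---|---|---|---|---|---|
| A | 30% | 1.5 | 91.8% | 92.2% | 0.4 |
| A | 30% | 2 | 91.4% | 92.7% | 1.3 |
| A | 30% | 3 | 91.6% | 95.5% | 3.9 |
| A | 50% | 1.5 | 91.2% | 91.3% | 0.1 |
| A | 50% | 2 | 91.1% | 92.5% | 1.4 |
| A | 50% | 3 | 91.0% | 94.2% | 3.2 |
| B | 30% | 1.5 | 88.9% | 90.0% | 1.1 |
| B | 30% | 2 | 88.4% | 89.7% | 1.3 |
| B | 30% | 3 | 84.4% | 89.7% | 5.3 |
| B | 50% | 1.5 | 90.0% | 90.7% | 0.7 |
| B | 50% | 2 | 88.2% | 89.4% | 1.2 |
| B | 50% | 3 | 86.0% | 90.7% | 4.7 |

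With a covariate hazard ratio of 1 (set B) there is no gain: 88.6% v 88.5% and 88.7% v 88.3%. Type I error in set B was about 4 to 5% with and without the covariate.

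**3. Where the gain comes from.** Under the set A assumptions the mean standard error of the treatment log hazard ratio was 0.1457 to 0.1459 without the covariate and 0.1459 to 0.1463 with it, so it did not shrink. The estimate moved further from 1: from about 0.619 to 0.611 at covariate hazard ratio 2, and from about 0.62 to 0.595 at 3. In set B the model without the covariate gave about 0.65 at hazard ratio 3, where the conditional value was 0.63.

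**4. Chance imbalance.** Assume 40% prevalence and 544/2 = 272 per arm.

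- 2 SD of the difference in proportions: 2 × √(2 × 0.4 × 0.6/272) = 0.084, about 8 percentage points.
- Approximate shift in the log hazard ratio at covariate hazard ratio 2: 0.084 × ln 2 = 0.058, a factor of about 1.06.
- Against a standard error of 0.146 (460 participants): 0.058/0.146 = 0.40. With 544 × 0.425 = 231 events the standard error is about 2/√231 = 0.132, and the ratio is 0.44.
- A borderline z of 1.96 would become about 1.56 or 2.36 (p about 0.12 or 0.02), depending on the direction of the imbalance.
- Range for an imbalance at the 95% limit, prevalence 30% to 50%: a factor of about 1.03 at hazard ratio 1.5, 1.06 at 2, and 1.09 to 1.10 at 3.

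**The case against.** The plan already names the proposed model as supportive analysis 5, so the change mostly exchanges two labels. Adjusting for the stratification factor and pilot membership is a legitimate prespecified choice. The SAP's target comes from marginal proportions, which the less-adjusted model matches more closely, and in set A that model already exceeds 90% power. The SAP is also the final version, dated after follow-up ended. All of this stands, and it limits the point to a modest improvement.

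A reader might draw three stronger conclusions, none of which the document supports.

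- *The primary analysis is biased or underpowered.* Randomisation and the confidence interval already allow for chance imbalance, type I error holds, and the sample size reproduces.
- *The plan makes the less precise estimate its main result.* Adjustment does not reduce the standard error in this Cox model. The two hazard ratios are conditional on different covariates, so some difference between them is expected.
- *Prior admission is an established strong predictor that the trial already holds in full.* The SAP gives no prognostic strength. In first-episode psychosis an admission in the preceding six months may simply be the index episode. The Baseline list under Data collection does not name the variable, and the informatics data described cover the period after baseline. Item 5 implies that the variable is available, but not its source or completeness. The health economic section expects some missing baseline resource use.

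The objection does not remove two things: item 5 is optional as worded, and there is no rule for reading a disagreement between it and the primary result.

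**Conclusion.** The point holds as a small gain in efficiency and robustness, not as an error or contradiction. Power would rise by about 0 to 1 point at a covariate hazard ratio of 1.5, about 1 to 1.5 points at 2 and about 3 to 5 points at 3, and not at all if prior admission is not prognostic. Protection against a 2-SD imbalance is worth about 6% on the hazard ratio, or 0.4 of a standard error, at hazard ratio 2 and 40% prevalence. These sizes rest on assumed prevalence and prognostic strength, a binary covariate, constant hazards and no clustering. The direction of the effect depends only on prior admission being prognostic, which is plausible for this outcome but not documented.

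**What to change.** While the statisticians are still blind:

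1. In Analysis of the primary outcome, add admissions in the six months before baseline to the Cox model beside cannabis severity and pilot membership. State the form, for example 0, 1, 2 or more, with a category for unknown so that no participant is dropped.
2. Replace item 5 with the present two-covariate model, as an analysis that will be done.
3. State that some difference between the two hazard ratios is expected from non-collapsibility and is not in itself evidence against either.
4. Name the source of the variable and check its completeness, without reference to allocation, before fixing the form.

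The cost is a dated SAP revision, one to three extra parameters against roughly 196 planned events, and a hazard ratio conditional on one more covariate. If the primary model is to stay as it is, the least change is to make item 5 a firm commitment, with its form, its missing-value rule and a sentence on how a discrepancy will be read.

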These will be analysed separately for data collected at 12 weeks and 18 months. Models will include severity of cannabis use at baseline and whether the participant was part of the pilot trial. For the dichotomous outcomes (cannabis positive urine, engaged in work or study), logistic regression with robust standard errors to account for clustering by therapist will be used. If there are too few participants engaged in work or study for logistic regression to be possible then results will be reported descriptively. For continuous outcomes (positive and negative symptoms), linear regression with robust standard errors will be used.

For count outcomes, Poisson regression with robust standard errors will be used for count outcomes (number of cannabis days and number of admissions over follow up). If there are excess zeros for either count outcome, then the use of zero inflated Poisson regression will be explored.

Appropriate estimates and 95% confidence intervals will be presented for all analyses.

Missing data

There is not much missing data for the primary outcome since it is an objective outcome collected from the appropriate informatics departments.

There is missing data for other variables, especially at follow up. This may be because of non-attendance at the follow up appointment or non-response to specific questions. The extent and patterns of missingness will be assessed. Potential predictors of missing values that are related to the outcomes will be identified. .

Multiple imputation¹⁶ may be used if it is felt to be necessary. We will only impute outcome data if surrogate outcomes or variables closely related to the missing outcome(s) are available. Otherwise there is no gain in imputing outcomes¹⁷.

The primary analysis will be complete case analysis with analysis using multiple imputation being a supportive analysis if it is carried out.

Supportive analyses

There will be up to six supportive analyses for the primary outcome:

1. Analysis of all outcomes with their baseline predictors of missingness, that is modelling including the randomised allocation, whether the participant was in the pilot trial and the level of cannabis use at baseline

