The objective of the cost effectiveness analysis is to establish the relative cost-effectiveness of contingency management versus optimised treatment as usual at 18 months. The primary outcome will be QALYs (Quality Adjusted Life Years) calculated using EuroQol EQ-5D (3L) health profiles combined with health state preference values from the UK general populationⁱ. The resultant mean Quality of Life utility scores of the two treatment groups will be compared at eighteen months using unpaired *t*-tests. QALYs will be calculated using the area under the curve method and compared between groups adjusting for baseline EQ-5D utility scoresⁱⁱ.

Costs will be calculated based on resource use gathered from an adapted version of the client services receipt inventory (CSRI)ⁱⁱⁱ. The primary analysis will take an NHS and personal social services perspective^{iv}.

Costs of the contingency management intervention and optimised treatment as usual will be calculated using the salaries of staff delivering the intervention, plus employer on-costs, overhead costs, the cost of providers of supervision, and the cost of any equipment or consumables. A ratio of direct face-to-face to indirect non-face-to-face time will be applied.

Total costs at 18 months will be calculated by combining resource use with unit costs at 2016 prices. Unit costs will be derived from PSSRU and NHS reference costs. Medications will be costed using NHS prescription cost analysis data. Costs and QALYs will be discounted at 3.5% per year.

Costs will be compared, adjusting for baseline differences. Patient level costs and quality of life data will be bootstrapped with replacement (N = 10,000) to populate incremental cost effectiveness (ICER) planes, to estimate median cost-effectiveness and (pseudo) 95% confidence intervals. The probability of the intervention being cost-effective at different levels of willingness to pay for health benefits will be shown by generating cost-effectiveness acceptability curves (CEACs).

No subgroup health economics analyses are planned. The CHEERS statement will be completed^v.

Additional health economics analyses

1. Cost effectiveness at 3 months will be reported.
2. Results from a broader perspective including costs from criminal justice and cost of unpaid lost productivity due to illness will be reported.
3. Cost-effectiveness using alternative outcomes will be reported:
 - QALYs calculated using SF-12 data
 - Time to relapse (to 18 months)

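### The economic section names neither the randomisation stratum nor the pilot term, and does not say that the adjusted models are refitted in each bootstrap replicate, so the CEAC may depart from the adjusted results

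*SAP*

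**What the plan says.** Randomisation section: allocation was "stratified by severity of cannabis use (one to three times a week versus four or more times a week").

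Analysis of the primary outcome: the Cox model is fitted "adjusting for severity of cannabis use at baseline (the stratification variable, dichotomous") and for pilot participation. For the secondary outcomes, "Models will include severity of cannabis use at baseline and whether the participant was part of the pilot trial".

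Health Economic analyses section:

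- Utility: the mean "utility scores of the two treatment groups will be compared at eighteen months using unpaired" t-tests, with no covariate.
- QALYs: area under the curve, compared with adjustment for baseline EQ-5D utility. No other covariate is named.
- Costs: "Costs will be compared, adjusting for baseline differences". No variable is named.
- Uncertainty: "Patient level costs and quality of life data will be bootstrapped with replacement (N = 10,000) to populate incremental cost effectiveness (ICER) planes". The same sentence takes the median cost-effectiveness and the pseudo 95% intervals from this bootstrap. The CEACs follow in the next sentence.

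Nothing is said about refitting the adjusted models within replicates, resampling within arm, or keeping each participant's cost and QALY together.

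**The concern.** The probability of cost-effectiveness is a main economic result, and the SAP takes it from the bootstrap. The SAP commits to removing baseline imbalance from the QALY and cost differences. It does not carry that commitment into the step that produces the plane, the intervals and the CEAC. Two competent analysts could follow the text and draw different curves: one from raw arm means of the resampled records, the other from regression coefficients re-estimated in each resample. The first would bring back the imbalance that the adjusted differences remove, and would use a larger QALY variance.

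The economic models as described also omit the factor on which the trial stratified its randomisation. For costs, they leave the covariates to be chosen later.

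**Working it through.** **The SAP's own figures.** The SAP gives no numerical target for the economic analysis. The figures that bear on the point come from its Sample size section. The clustering factor is 1 + (4 - 1) x 0.02 = 1.06, and 460 x 1.06 = 487.6, or 488, as stated. The recruitment target of 544 gives 544 / 2 = 272 per arm.

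**Inputs for the size of the effect.** From the SAP: 272 per arm (equal arms, everyone contributing data), EQ-5D at baseline, 12 weeks and 18 months (78 weeks), and QALYs by area under the curve. Assumed, because the SAP gives no figure: utility SD 0.20-0.30, slope of follow-up utility on baseline utility 0.3-0.7, and GBP 20,000 per QALY. Discounting is ignored.

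**Step 1: size of a chance imbalance.** SE of the baseline difference = SD x sqrt(2/272) = SD x 0.0857.

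- SD 0.20: 0.017
- SD 0.25: 0.021
- SD 0.30: 0.026

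**Step 2: carry-over to QALYs.** The trapezoid rule on 0-12 and 12-78 weeks gives baseline a weight of 6/78 and the two follow-ups together 72/78. Shift in the unadjusted QALY difference = imbalance x (6/78 + slope x 72/78) x 1.5 years.

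| SD | Slope | Imbalance (1 SE) | Multiplier | QALY shift | At GBP 20,000 |
|---|---|---|---|---|---|
| 0.20 | 0.3 | 0.0171 | 0.354 x 1.5 = 0.531 | 0.009 | about GBP 180 |
| 0.25 | 0.5 | 0.0214 | 0.538 x 1.5 = 0.808 | 0.017 | about GBP 346 |
| 0.30 | 0.7 | 0.0257 | 0.723 x 1.5 = 1.085 | 0.028 | about GBP 560 |

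**Step 3: precision.** If baseline utility correlates 0.4-0.6 with QALYs (assumed), adjustment removes 0.4² = 16% to 0.6² = 36% of the QALY variance. A bootstrap of raw means does not have this gain.

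**Step 4: illustration on the CEAC.** One data set was simulated for each imbalance, with 272 per arm, utility SD 0.3, QALY slope 0.75 on baseline utility and residual SD 0.25. The adjusted QALY difference was 0.02 and the adjusted cost difference GBP 300, with skewed costs and GBP 20,000 per QALY. The adjusted net benefit is therefore 20,000 x 0.02 - 300 = GBP 100.

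| Baseline utility imbalance | P(cost-effective), raw bootstrap | P(cost-effective), models refitted |
|---|---|---|
| 0.00 | 0.54 | 0.53 |
| 0.02 | 0.62 | 0.53 |
| 0.04 | 0.71 | 0.54 |

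At SD 0.3 one SE is 0.026, so the last two rows are about 0.8 and 1.6 SE. All inputs are assumed, so the table shows direction and rough size only.

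**Step 5: therapist clustering.** If whole therapist clusters sat in one arm, ignoring the factor of 1.06 would make the SE too small by sqrt(1.06) = 1.03, and a nominal 95% interval would cover about 94.3%. Here, participants were individually randomised. If the therapist is the care coordinator, clusters cross arms and a shared therapist effect largely cancels. Simulating 136 therapists with 4 participants each, and no therapist-by-arm effect, gave variance ratios of 0.99 at ICC 0.02 and 1.00 at ICC 0.10. Interval coverage was 95.1% and 94.8%.

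**The case against.** The strongest reply is that the SAP never says the bootstrap is unadjusted. Resampling patient records is also the first step of a bootstrap that refits the adjusted models, and the bootstrap sentence directly follows the one on adjusted costs. A reader might infer that raw means are planned, but the text does not support that. What stands is that the step is left open. The section contains one comparison with no covariates (the t-test on utility) beside two adjusted ones, so adjustment cannot simply be presumed.

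Four further limits on the point are fair.

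- A reader might conclude that the adjusted differences and the CEAC would estimate different quantities. They would not: under randomisation, the raw and the linearly adjusted mean differences have the same target. They differ in precision and in chance imbalance.
- Naming no variables for costs does not exclude the stratum or the pilot term. The missing-data item under Additional health economics analyses also refers to baseline resource use and other covariates, so more terms may be intended. They are still not named.
- A reader might see the absence of therapist clustering as a serious flaw, since the SAP specifies "Robust standard errors will be used to account for clustering by therapist" in the primary analysis. Step 5 shows that it is minor at the SAP's own inputs. The SAP's text on continuous outcomes, the nearest analogue to costs and QALYs, also mentions only robust standard errors, without naming therapist.
- No figure in the SAP shows how much the stratum and pilot terms would change the economic results. The case for them is that the analysis should reflect the randomisation and match the clinical models.

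**Conclusion.** The point holds as a free improvement. The SAP names baseline utility as the only covariate for QALYs and none for costs. It omits the stratum and pilot indicator, and does not tie the bootstrap to the adjusted models. On a literal reading, an ordinary one-SE baseline imbalance could move the QALY difference behind the CEAC by about 0.009-0.028, or about GBP 180-560 per person, away from the adjusted difference reported beside it. These sizes depend on the assumed SD, slope and willingness to pay, on 272 per arm with complete data, and on the bootstrap being done without refitting. If the analysts already intend to refit, the discrepancy does not arise and only the wording needs to change.

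**What to change.** Replace the relevant sentences of the Health Economic analyses section with text to this effect:

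*The cost regression includes arm, baseline cost, cannabis severity stratum and pilot indicator. The QALY regression includes arm, baseline EQ-5D utility, cannabis severity stratum and pilot indicator. In each of the 10,000 bootstrap replicates, participants are resampled with replacement within arm, each participant's cost and QALY are kept as a pair, and both regressions are refitted. The two arm coefficients from each replicate give the cost-effectiveness plane, the intervals and the CEAC.*

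Resampling by therapist is not needed for this purpose.

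The cost is a few sentences and a few lines of code. The SAP lists EQ-5D and the CSRI among its baseline measures, and the stratum and pilot indicator are already used in the clinical models, so no new data are required. The change is best made while the health economists are still blind to allocation.

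### The SAP's median cost-effectiveness, most naturally the median bootstrap ICER, can be wrong in size or sign when replicates span quadrants

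*SAP*

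**What the plan says.** The relevant text is in the SAP, Health Economic analyses. Patient-level costs and quality of life are to be "bootstrapped with replacement (N = 10,000) to populate incremental cost effectiveness (ICER) planes", and the purpose of the replicates is "to estimate median cost-effectiveness and (pseudo) 95% confidence intervals". Acceptability curves over a range of willingness to pay follow in the next sentence.

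The two increments are also handled separately. QALYs are compared between arms with adjustment for baseline EQ-5D utility, and for costs the SAP says "Costs will be compared, adjusting for baseline differences".

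The section does not define median cost-effectiveness or say how the pseudo interval is formed. It mentions neither an ICER computed from mean differences nor net monetary benefit, and it has no rule for replicates that fall in different quadrants.

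**The concern.** Cost-effectiveness is a ratio of increments, and the sentence ties the median to the ICER plane. The plan therefore reads most naturally as the median of the replicate ratios, with an interval taken from the same replicates. On that reading it is the only point estimate and interval for cost-effectiveness itself that the SAP states.

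Such ratios are not ordered. A negative value can mean cheaper and better, or dearer and worse. A given positive value is good news on one side of a zero QALY difference and the opposite on the other, and the ratio grows without bound as the QALY difference approaches zero. The decision quantity is mean incremental cost divided by mean incremental QALY, and a median of ratios does not estimate it.

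At stake is the stated objective of the economic analysis, the relative cost-effectiveness of the two arms at 18 months. The reported figure and interval could be wrong in size or sign, and could disagree with the acceptability curve drawn from the same replicates.

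**Working it through.** The SAP states no ICER, variance or threshold, so there is no plan figure to reproduce. The check asks how the likeliest statistic behaves. Write dC for the cost difference and dQ for the QALY difference.

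**1. Mirror case.** Changing the sign of both dC and dQ in every replicate leaves every ratio unchanged, because (-dC)/(-dQ) = dC/dQ. The median and any interval from the ratios are then identical for opposite results. Assumed inputs:
- dQ = 0.02, dC = -£1,000, zero correlation;
- SDs of 0.35 QALY and £15,000;
- 245 per arm, roughly half of the 488 in the SAP's Sample size section.

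The SEs are 0.35 × √(2/245) = 0.032 and 15,000 × √(2/245) = £1,355. In 10,000 draws the median ratio is -£17,048, both as drawn and with all signs reversed. The probability of being cost-effective at an assumed £20,000 per QALY is 0.83 in the first case and 0.17 in the second.

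**2. Median against ratio of means.** Assumed inputs: dC = £300 (SE £1,000), QALY SE 0.03, zero correlation, normal approximation to the bootstrap distribution. The ICER is 300/dQ, and the share of replicates below zero QALYs is Φ(-dQ/0.03). Medians are simulated, with run-to-run error of about £100 or less.

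| dQ | dQ in SEs | Share with dQ < 0 | ICER | Median ratio (about) |
|---|---|---|---|---|
| 0.01 | 0.33 | 37% | £30,000 | £3,200 |
| 0.02 | 0.67 | 25% | £15,000 | £5,200 |
| 0.05 | 1.67 | 4.8% | £6,000 | £5,300 |
| 0.06 | 2.00 | 2.3% | £5,000 | £4,700 |
| 0.10 | 3.33 | 0.04% | £3,000 | £3,000 |

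**3. Interval.** If the pseudo interval were the 2.5 and 97.5 percentiles of the ratios, it would be about -£415,000 to £420,000 at dQ = 0.01. At dQ = 0.06 it would still be about -£58,000 to £83,000.

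**4. Quadrants at dQ = 0.01.** P(dQ < 0) = Φ(-0.333) = 0.369 and P(dC < 0) = Φ(-0.3) = 0.382.
- Cheaper and better: 0.382 × 0.631 = 0.24.
- Dearer and worse: 0.618 × 0.369 = 0.23.

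So about 47% of ratios are negative, split almost evenly between opposite conclusions.

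**5. Sign.** At dQ = 0.01 the ICER is +£30,000. With a cost-QALY correlation of -0.3 the median is about -£5,700. With +0.3 it is about £12,100.

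**6. Agreement with the acceptability curve, dQ = 0.01, zero correlation.** About 65% of the ratios lie below £20,000. Net benefit at £20,000 has mean 20,000 × 0.01 - 300 = -£100. Its SE is √(20,000² × 0.03² + 1,000²) = √1,360,000 = £1,166. The acceptability curve therefore gives Φ(-100/1,166) = 0.466, from the same replicates.

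**7. Net benefit as the alternative.** The 95% interval is -100 ± 1.96 × 1,166, or about -£2,390 to £2,190. In the mirror pair, simulated separately, net benefit is about +£1,407 (-£1,487 to £4,374) and -£1,404 (-£4,315 to £1,522), so it separates the two cases.

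**The case against.** The strongest reply is that a reader of the results would not depend on the median alone. The plane shows how replicates spread over quadrants, the acceptability curve is unaffected by the ordering problem, and adjusted cost and QALY comparisons are already planned. That is correct and narrows the point. It does not repair the one estimate and interval of cost-effectiveness that the SAP states, and step 6 shows that the ratios and the curve can point in different directions.

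The second reply is that the harm depends on unknown values. This also stands. The median's bias largely disappears once the QALY difference is about 2 SE. The interval criticism lasts longer, as the limits at 0.06 show.

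Three stronger readings are tempting:
- A reader might infer that the SAP makes the median ICER its headline result with percentile limits. It uses none of these terms, and the word pseudo suggests that its authors know the interval is not a conventional one.
- A reader might infer that the result will mislead. The SAP gives no effect sizes or variances from which that could follow.
- A reader might want the bootstrap clustered by therapist, as the clinical models are. The Sample size section's design effect of 1.06 would widen SEs by √1.06 = 1.03, about 3%, if it applied to costs and QALYs. Participants are randomised individually and optimised usual care goes to both arms, so a care coordinator may have participants in each, and resampling by therapist within arm would break that link. The documents do not support that request.

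**Conclusion.** The point holds in conditional form. The SAP's summary is undefined and, on its likeliest reading, unsound when replicates span quadrants. The mirror case shows this whatever the effect size: one median can describe two opposite results. Under the assumed inputs the median runs from about a tenth of the ICER (£3,200 against £30,000) to full agreement (£3,000), and a negative cost-QALY correlation can reverse its sign. The cost difference, SEs, correlation and £20,000 threshold are all assumptions. If another meaning of median cost-effectiveness was intended, the phrase still needs a definition. The primary clinical analysis is untouched.

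**What to change.** In Health Economic analyses, replace the median and its pseudo interval with the following:
- The ICER is the adjusted mean incremental cost divided by the adjusted mean incremental QALY.
- Uncertainty is given as a 95% interval for incremental net monetary benefit at stated willingness-to-pay values, beside the acceptability curve and plane already planned.
- No ICER interval is reported when replicates span quadrants.
- Each patient's cost and QALY stay paired when resampling within arm.

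The cost is SAP wording; no new data are needed. The one downside is that net benefit depends on a threshold, which must be stated in advance; giving several values limits this.
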